5. SUBJECTS IN THE PROJECT: a. State the inclusion and exclusion criteria for enrollment of subjects. Inclusion factors for the patient group will be subjects who have Insomnia and have opted for behavioral treatment for insomnia as therapy at recruitment. Exclusion criteria for subject group includes the presence of unstable chronic medical conditions or mental health conditions that would interfere with the study protocol as well as the presence of moderate depression (QIDS > 15) at recruitment. The history of sleep disorders other than insomnia by self-report will be assessed and used as covariates in analyses; subjects presenting with a history consistent with obstructive sleep apnea (OSA) or restless leg syndrome (RLS) or other sleep disorders will be identified based on standardized questionnaires. b. Describe the control population (if utilized) and justify its selection. The control for this study will be an "information control" treatment group. Subjects will be emailed sleep tips and sleep-related information. c. Support the likelihood of recruiting the number of subjects required to complete the project. Relate this to other projects recruiting similar subjects. Participants will be recruited from several well-developed sources, including the HFHS Sleep Center Clinical database. We maintain a large and representative database (N=7608) of prior participants who have volunteered to be contacted for clinical trials. Preliminary analyses suggest that a large proportion of this database (N=2590) meets primary inclusion criteria for this proposal (current insomnia but no depression). These individuals will be contacted by phone and/or email for potential participation pending a screening assessment. We believe that based on the success we have seen in previous studies (IRB#5544 and #8447), we will be able to complete this protocol within two years following IRB approval.

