7. DATA ANALYSIS: Describe the analysis of the data and relate this to the specific aims in detail. Case reports and medical record reviews also require a description of the planned data analysis (ie. descriptive, observational). The Committee recommends free consultation with the Division of Biostatistics and Research Epidemiology before IRB submission. The following data analysis plan was developed in conjunction with [name], biostatistics section. A logistic regression will be used to assess the association between treatment group and depression status at 1 year. This approach allows inclusion of covariates in the model. We plan on enrolling a total of 300 subjects per group. This results in the analysis having 85% power, with a two-sided alpha level of 0.05, to detect an odds ratio of 2.7 corresponding to rates of depression at 1 year of 10% and 4%. Stratified analysis assuming an equal split of the population, will have 85% power to detect an odds ratio of 10.0. This corresponds to a difference in rates from 10% to 1% which is what we anticipate.

8. JUSTIFICATION FOR NUMBER OF SUBJECTS OR DATA: a. State the number of subjects or data points to be analyzed in the project at this institution and the total number for multicenter studies. The Committee recommends consultation with the Division of Biostatistics and Research Epidemiology [contact]. The proposed sample size of 300 per group (n=600) will yield > 85% power to detect effects with a two-tailed 0.05 alpha level. b. Describe the statistical justification for this number of subjects or data points. The primary hypothesis i.e., risk of depression incidence in the dCBT group relative to the control group will be analyzed using a multivariate logistic regression model. Group differences in continuous outcomes (e.g., SOL, TST, WASO; see STRATEGY section for a full list of quantitative measures) will be tested using ANCOVA models. Power. We anticipate a 14.6% rate of incident depression in the control group, compared to 6.7% in the treatment group.²¹ The proposed sample size of 300 per group (n=600) will yield > 85% power to detect effects with a two-tailed 0.05 alpha level.

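### The primary logistic model names no depression-severity covariate, although QIDS is scored at entry; prespecifying it would give a modest power gain without new data

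*Combined protocol and SAP*

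**What the plan says.** - **Entry score.** Section 5a excludes "the presence of moderate depression (QIDS > 15) at recruitment". Every screened participant should therefore have a QIDS value, and scores up to 15 can enter.
- **Primary model.** Section 7 plans a logistic regression relating treatment group to depression status at 1 year and adds: "This approach allows inclusion of covariates in the model". Section 8b calls the model for the primary hypothesis multivariate. Neither section lists the terms.
- **Named covariates.** The only commitment is in section 5a: "The history of sleep disorders other than insomnia by self-report will be assessed and used as covariates in analyses".
- **Design.** Section 6a describes a randomised parallel-group study and mentions no stratification.
- **Size.** "We plan on enrolling a total of 300 subjects per group" (section 7). Section 7 claims 85% power at 10% vs 4%, "with a two-sided alpha level of 0.05". Section 8b gives other rates: "We anticipate a 14.6% rate of incident depression in the control group, compared to 6.7% in the treatment group", and says that 300 per group "will yield > 85% power to detect effects with a two-tailed 0.05 alpha level".

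**The concern.** How depressed a participant is at entry is the obvious candidate predictor of depression a year later, whichever instrument defines the outcome. The plan already collects a score for it but commits only to sleep-disorder history as a covariate. Three things are at stake.

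- **Power.** Few events are expected: 300 × 0.10 = 30 and 300 × 0.04 = 12. The section 7 scenario has little slack, and no dropout rate is given.
- **Chance imbalance.** No stratification is described, so the text contains nothing that balances entry severity by design.
- **Prespecification.** An open covariate list lets the primary model be settled after the data are seen.

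**Working it through.** **1. The plan's own power.** Inputs: 300 per group and two-sided alpha 0.05 (section 7), with the rates from sections 7 and 8b. With p̄ the mean of the two rates, the pooled formula is

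power = Φ{[(p1 − p2) − 1.96·√(2p̄(1 − p̄)/n)] / √([p1(1 − p1) + p2(1 − p2)]/n)}

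- 10% vs 4%: p̄ = 0.07. (0.06 − 1.96 × 0.02083)/0.02069 = 0.93, so power is 82.3%. The odds ratio is (0.10/0.90)/(0.04/0.96) = 2.67. The arcsine method gives 83.9%, and an odds ratio of exactly 2.7 on a 4% rate gives 83.4%. The stated 85% is thus matched to within 2 points by these variants. By the pooled formula at exactly 10% vs 4%, 85% needs 324 per group.
- 14.6% vs 6.7%: p̄ = 0.1065. (0.079 − 1.96 × 0.02519)/0.02498 = 1.19, so power is 88.2%, which agrees with the claim in section 8b.

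**2. Power with entry QIDS, latent-score model.** Assumptions, none from the documents: entry QIDS is Normal(8, 4.5) truncated to 0-15 (SD about 3.58); the 1-year latent score correlates 0.4, 0.5 or 0.6 with it; thresholds are set so that the marginal rates equal the plan's. Wald test, 300 analysed per arm.

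| Rates | Unadjusted | Adjusted |
|---|---|---|
| 10% vs 4% | about 82-84% | about 84-87% |
| 14.6% vs 6.7% | about 88-89% | about 90-92% |

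With the marginal rates fixed, unadjusted power cannot depend on the correlation. The spread in that column is simulation error: with 4,000 trials, √(0.83 × 0.17/4000) is about 0.6 points. The gain is about 2 to 4 points.

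**3. The same question, logistic model.** Here the assumption is an odds ratio per SD of entry QIDS of 1.5, 2 or 3. Likelihood-ratio test, 4,000 trials per scenario.

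| Odds ratio per SD | Power, 10% vs 4% | Power, 14.6% vs 6.7% | SE of log OR, 10% vs 4% | Conditional OR, 10% vs 4% | Variance efficiency, risk difference (10/4; 14.6/6.7) |
|---|---|---|---|---|---|
| 1.5 | 83.4 → 83.6% | 89.7 → 90.1% | 0.355 → 0.358 | 2.69 | 1.01; 1.01 |
| 2 | 84.2 → 85.1% | 89.0 → 90.1% | 0.356 → 0.363 | 2.75 | 1.03; 1.05 |
| 3 | 83.6 → 86.5% | 89.4 → 92.9% | 0.357 → 0.374 | 2.92 | 1.09; 1.14 |

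The gain runs from near zero to about 3.5 points. The standard error of the log odds ratio rises with adjustment. Power increases because the conditional odds ratio moves further from 1 than the standard error grows. In the last row, ln(2.67)/0.357 = 2.75 becomes ln(2.92)/0.374 = 2.87. Precision itself improves only on the risk-difference scale, by 1 to 14% in variance efficiency.

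**4. Chance imbalance.** The 95% limit for a difference in mean entry score between arms is 1.96 × √(2/300) = 0.16 SD, or 0.16 × 3.58 = 0.57 points under the SD assumed in step 2.

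- An imbalance at that limit multiplies the unadjusted odds ratio by about 1.5^0.16 = 1.07, 2^0.16 = 1.12 or 3^0.16 = 1.19.
- In the latent-score model it moves a 10% rate to 11.2-11.8%, that is by 1.2-1.8 points, or 20-30% of the planned 6-point difference.
- An imbalance of one standard error does about half as much.

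**The case against.** **The plan does not exclude entry QIDS.** A reader might infer that the primary model leaves it out. The documents do not support that: section 7 allows covariates and section 8b says multivariate. The plan also points to material not in the text (a strategy section and an appendix), which may list them. This stands, so the point is that entry QIDS is not named. Permission to adjust is still not prespecification.

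**The link between entry score and outcome is not in the documents.** It is tempting to argue that someone entering at 15 is one point from being a case and someone entering at 3 is 13 points away. QIDS > 15 appears only as an exclusion, and the text does not define 1-year depression or say that QIDS measures it. That argument is therefore inference and is not relied on. The case needs only that entry severity predicts later depression. Adjustment would not repair an undefined endpoint either.

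**Adjustment does not make the odds ratio less noisy.** Correct, as step 3 shows. The benefit lies in power and on the risk-difference scale.

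**Chance imbalance is already paid for.** The unadjusted standard error and test allow for it under randomisation, and the 20-30% figure is the 95% limit. This also stands: the imbalance figures show how far a single trial's estimate can be carried, not a bias, and they should not be added to the power gain.

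**The gain is small and rests on assumptions.** True. The recruitment pool is described in section 5c as having no current depression, so entry scores may be lower than assumed here. At 14.6% vs 6.7% power exceeds 85% without adjustment. Against this, the change is almost free, and under a moderate or strong association it brings the 10% vs 4% scenario to about the stated 85%.

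**Conclusion.** The concern holds in a limited form. The plan does not prespecify entry QIDS in its primary model, although the score is collected and is plausibly a strong predictor. The cost is some efficiency and an open covariate list. A reader might go further and call the planned treatment estimate biased, but randomisation rules that out.

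The expected gain is about 2 to 4 points of power if entry and 1-year severity correlate at 0.4 to 0.6, and near zero if QIDS is only weakly prognostic. The estimate is also protected from chance imbalance in entry severity. The prognostic strength and the entry distribution are assumptions, and all figures take 300 analysed per arm. The amendment is worth making because it costs so little, but the validity of the trial does not depend on it.

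**What to change.** In section 7, state that the primary logistic regression of 1-year depression status contains treatment group, entry QIDS as a continuous covariate, and the sleep-disorder covariates of section 5a. Make section 8b refer to the same model.

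State that the odds ratio from this model is conditional, and report beside it a standardised risk difference: the mean predicted risk over all participants under each arm, subtracted, with a confidence interval. The result can then be set against the planned 10% vs 4% or 14.6% vs 6.7%, which are marginal rates. The conditional odds ratio is not directly comparable with the planned 2.7.

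The cost is a sentence or two of text. The entry score already exists, so no data, visits or participants are added, and the sample size can stay as it is.

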6. PROJECT DESIGN AND PROTOCOL: a. Describe the experimental design/methodology. This is a randomized parallel group study with group 1 getting CBT-I treatment for insomnia by an online program (Sleepio) and group 2 getting information control sleep tips. Insomnia and other sleep-related symptoms will be assessed at pre treatment, post treatment and at 1-year follow-up. Sleepio can be accessed at www.sleepio.com. Click "Log In" at top right corner and enter email "[contact]" and password "password". b. Outline the protocol, corresponding it to the specific aims; identify the data or endpoints to be analyzed to reach the specific aims. Our primary aim is to maximize and/or improve sleep efficiency in patients (number of hours asleep over number of hours in bed) and to shorten sleep latency (amount of time taken to fall asleep). The primary aim will be to reduce the incidence of depression. Other secondary measures will be taken regarding aspects other than sleep in patients. These will be recorded through the surveys mentioned above and will measure symptom improvements in severity of depression and work productivity. c. Discuss potential limitations and difficulties in the protocol. We do not anticipate any limitations to the current protocol. d. Provide a tentative schedule for conducting and completing this project and, if applicable, the multicenter study. We plan on starting data collection between February 25 and March 1, pending IRB approval. e. Data collection: Submit a copy of the data collection tool or list the data fields to be collected (review IRB policy, Access to Medical Records for Research).Attached in appendix.

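### Sections 7 and 8 justify 300 per group for the primary logistic regression with two unreconciled pairs of depression rates, and Section 7 attaches its 85% power to 300 enrolled with no allowance for loss by 1 year

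*Combined protocol and SAP*

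**What the plan says.** Section 7 (Data Analysis) defines the primary analysis: "A logistic regression will be used to assess the association between treatment group and depression status at 1 year". It then gives the size: "We plan on enrolling a total of 300 subjects per group". The power claim built on that size reads: "This results in the analysis having 85% power, with a two-sided alpha level of 0.05, to detect an odds ratio of 2.7". Section 7 derives this odds ratio from 1-year depression rates of 10% in one group and 4% in the other. For the stratified analysis that follows, it describes a fall from 10% to 1% as the anticipated result.

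Section 8b (statistical justification) takes up the primary hypothesis again: "risk of depression incidence in the dCBT group relative to the control group will be analyzed using a multivariate logistic regression model". Its rates are different: "We anticipate a 14.6% rate of incident depression in the control group, compared to 6.7% in the treatment group". Both 8a and 8b conclude: "The proposed sample size of 300 per group (n=600) will yield > 85% power to detect effects with a two-tailed 0.05 alpha level".

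Section 6a sets the visits: "Insomnia and other sleep-related symptoms will be assessed at pre treatment, post treatment and at 1-year follow-up". No section in the file gives an expected loss by 1 year, a number expected to be assessed, or a rule for missing 1-year outcomes.

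**The concern.** The same 300 per group, for the same treatment comparison by the same type of model, rests on two pairs of rates, and no sentence says how they relate. The conflict reaches the anticipated rate without treatment. Section 7 expects 10% in its stratified sentence (its groups are not labelled, but the higher rate is naturally the control), and Section 8 expects 14.6%.

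The pairs also leave different room for loss. Section 7 states power on people enrolled, while the outcome is read a year later. If 10% versus 4% governs, there is little or no margin. If 14.6% versus 6.7% governs, there is some. This is the only sample-size justification in the file. Without a reconciled basis, a reader of a null result cannot tell which effect the trial was sized to find, or with what power.

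**Working it through.** **Inputs.** From Section 7: n = 300 per group, two-sided alpha 0.05 (z = 1.960), rates 0.10 and 0.04. From Section 8: the same n and alpha, rates 0.146 and 0.067. Covariates are ignored. Loss d is assumed at 5%, 10% and 20%. People not assessed are taken to contribute nothing, so n = 300(1 − d) = 285, 270, 240.

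**Odds ratios.** (0.10/0.90)/(0.04/0.96) = 2.67, stated as 2.7. (0.146/0.854)/(0.067/0.933) = 2.38.

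**Formulas.** Φ is the standard normal distribution function and p̄ the mean of the two rates.

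- Pooled: power = Φ[(p1 − p2 − z·s0)/s1], with s0 = √(2p̄(1 − p̄)/n) and s1 = √((p1(1 − p1) + p2(1 − p2))/n).
- Wald: power = Φ[ln(OR)/se − z], with se = √(1/(n·p1(1 − p1)) + 1/(n·p2(1 − p2))).
- Exact likelihood ratio: sum the binomial probabilities of all result pairs whose likelihood-ratio statistic is at least 3.841.

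**Section 7's figure, n = 300, 10% versus 4%.**

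- Pooled: s0 = 0.02083, s1 = 0.02069. (0.06 − 1.960 × 0.02083)/0.02069 = 0.927, so power is 82.3%.
- Wald: 0.9808/0.3519 − 1.960 = 0.827, so power is 79.6%.
- Exact likelihood ratio: 84.0%.
- Taking the odds ratio as exactly 2.7 with 4% fixed (10.11% versus 4%), the exact likelihood ratio gives 85.1% and the pooled formula 83.4%.
- The most favourable formula run is the log odds ratio with the null variance used throughout, se = √(2/(n·p̄(1 − p̄))). It gives 86.5%.

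**Section 8's figure, n = 300, 14.6% versus 6.7%.**

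- Pooled: s0 = 0.02519, s1 = 0.02498. (0.079 − 1.960 × 0.02519)/0.02498 = 1.186, so power is 88.2%.
- Wald: 0.8674/0.2829 − 1.960 = 1.106, so power is 86.6%.
- Exact likelihood ratio: 89.1%. Null variance: 90.6%. All exceed 85%.

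**Power under assumed loss (Wald / pooled / exact likelihood ratio / null variance).**

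| Assessed per group | 10% vs 4% | 14.6% vs 6.7% |
|---|---|---|
| 300 (none lost) | 79.6 / 82.3 / 84.0 / 86.5% | 86.6 / 88.2 / 89.1 / 90.6% |
| 285 (5%) | 77.5 / 80.3 / 82.0 / 84.8% | 84.8 / 86.6 / 87.4 / 89.1% |
| 270 (10%) | 75.3 / 78.2 / 80.0 / 82.8% | 82.9 / 84.7 / 85.6 / 87.5% |
| 240 (20%) | 70.3 / 73.2 / 75.2 / 78.3% | 78.3 / 80.3 / 81.6 / 83.4% |

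**Number assessed per group for 85% power.** In the same order: 347 / 324 / 309 / 287 for 10% versus 4%, and 287 / 273 / 264 / 251 for 14.6% versus 6.7%. By the first three methods the two pairs fall on opposite sides of 300. Tolerated loss for the second pair is 1 − n/300: 4.3%, 9%, 12% and 16.3%.

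**The case against.** The best defence is that Section 7 gives a detectable effect and Section 8 an expected one, which is common practice. On the risk-difference scale they fit: 6.0 points at about 85%, and an expected 7.9 points at more than 85%. Every method gives the second pair more power. This stands as far as it goes, and the larger odds ratio in Section 7 does not refute it, because power does not depend on the odds ratio alone. It fails on the untreated rate: Section 7 itself presents 10% as anticipated, in the stratified sentence, and Section 8 anticipates 14.6%.

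Four stronger readings are tempting, and the documents do not support them.

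- *The 85% is a miscalculation.* With complete follow-up, accepted methods come within about a point of it, and one formula exceeds it.
- *The two pairs describe two outcomes*, status at 1 year and incidence. Section 8 gives no time point, but the visit list in Section 6a concerns sleep symptoms, and 1 year is the only depression time point stated. Section 8's rates carry a citation, and Section 8 refers to a strategy section; neither source is in the file.
- *Section 8's power is also tied to enrolment.* The prompt in 8a asks for the number to be analysed, so its 300 may mean people assessed. Only Section 7 speaks of enrolling.
- *The trial is underpowered.* The documents give no loss rate. Under Section 8's rates, 20% loss still leaves about 80% by the pooled formula.

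It is also fair that the choice of method moves Section 7's power by about as much as the choice of rates. That is a reason to be cautious about the exact margin; it does not reconcile the rates.

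**Conclusion.** The point holds as an unreconciled planning basis together with an unstated assumption of complete follow-up. For 10% versus 4%, 85% is at best rounded up by the Wald, pooled and exact likelihood-ratio calculations (79.6% to 84.0%), with little or no margin; at 5% loss all four methods shown fall below 85%. For 14.6% versus 6.7%, the claim of more than 85% holds at 300 (86.6% to 89.1% by the same three methods) and survives a loss of between about 4% and 16%, depending on method; at 20% loss none of the four supports it.

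These figures rest on unadjusted comparisons, equal groups, loss rates that are assumptions, and no contribution from people not assessed. The contradiction in the anticipated rate depends on none of these. The point should be fixed, but it does not challenge the choice of 300 or the analysis.

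**What to change.** In Sections 7 and 8, state one pair of planning rates for the 1-year primary outcome. If the two pairs refer to different outcomes, say so and say which one the 300 rests on. Bring the anticipated 10% in the stratified sentence into line, or explain it. Then restate power on the number expected to be assessed at 1 year under a stated loss assumption, keeping 300 per group.

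Possible wording, with 20% as a placeholder for the sponsor's own figure: *300 will be enrolled per group. Assuming 20% are not assessed at 1 year, 240 per group give 80% power for 14.6% versus 6.7% [or 73% for 10% versus 4%], pooled two-proportion test, two-sided alpha 0.05.*

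The cost is a change of text and a somewhat lower stated power. No extra enrolment and no change to the analysis is needed.

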Sleep to prevent evolving affecting disorders (SPREAD)

NCT02988375

Approved on March 8th 2016

1. PURPOSE: State in one or two sentences the purpose or objective of this project. The purpose of this study is to determine the effectiveness of Digital Cognitive Behavior Therapy for Insomnia (dCBTI) in preventing the incidence of depression among individuals with insomnia.
2. SPECIFIC AIMS: Number your aims so that the aims can be referred to in the Project Design and Data Analysis sections of this outline. Specific aim 1: to assess the efficacy of dCBTI for the prevention of incident depression among individuals with insomnia. Specific aim 2: to determine the moderating effects of health/SES disparities on the efficacy of the dCBTI intervention.
3. RATIONALE FOR THE PROJECT: a. State the rationale for the project and support it with background information about the project. Critically evaluate existing knowledge, and specifically identify the gaps in knowledge the project will fill. A growing body of research indicates that treatment for insomnia may also help prevent the onset of depression (Falussy, Balla & Frecska, 2014). However, CBTI, the current first-line treatment for insomnia, is under-utilized due to a shortage of providers, time- and cost-constraints, and the stigma associated with mental-health treatment (Fields, Schutte-Rodin, Perlis & Meyer, 2013). Digital, internet-delivered forms of CBTI (dCBTI) can overcome these obstacles to make access more widespread, reduce health-care costs, and serve as a sustainable population-level prophylactic treatment for depression. b. State the applicant's prior research and experience in this research area. [name] has a broad background in clinical psychology, with specific training and expertise in sleep medicine. He is an Associate Editor for the journal SLEEP and has authored over 100 peer-reviewed original articles, reviews, and chapters, focused on sleep. He recently served as Chairman of the National Sleep Foundation. [name] has been funded by the NIH to study vulnerability to insomnia and triggers of insomnia (i.e. life stressors). [name] is board certified in CBT-I Treatment to successfully treat insomnia with the long-term goal of preventing incident depression. His experience in this area will make it possible to recruit and retain participants for this research study focusing on insomniacs and depression prevention efforts.

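### Aim 2 asks whether health/SES factors moderate the treatment effect, but the supplied analysis section states no comparison of that effect between strata, names no operational moderator, and leaves unclear what its 85% power refers to

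*Combined protocol and SAP*

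**What the plan says.** Section 2 lists two aims. The second is "to determine the moderating effects of health/SES disparities on the efficacy of the dCBTI intervention".

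Section 7, whose prompt asks for the analysis to be tied to the aims, gives this model: "A logistic regression will be used to assess the association between treatment group and depression status at 1 year". It adds "This approach allows inclusion of covariates in the model" and sets the size: "We plan on enrolling a total of 300 subjects per group". The only sentences on subgroups are "Stratified analysis assuming an equal split of the population, will have 85% power to detect an odds ratio of 10.0" and "This corresponds to a difference in rates from 10% to 1% which is what we anticipate". They are not linked to Aim 2, and the stratifying variable is not named.

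Section 8 adds a multivariate logistic model for the primary hypothesis and ANCOVA for continuous outcomes. The only covariate named in the supplied text is in section 5: "The history of sleep disorders other than insomnia by self-report will be assessed and used as covariates in analyses". That is an adjustment variable, not a stated moderator. Section 8 points elsewhere only for outcome measures ("see STRATEGY section for a full list of quantitative measures"), and section 4's counterpart on data collection, item 6e, refers to an appendix. Neither the STRATEGY section nor the appendix is supplied.

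**The concern.** Moderation means that the treatment effect differs between levels of another variable. Testing it needs a direct comparison of effects: an interaction term or a test of homogeneity of odds ratios. A main-effects logistic model does not contain that comparison. Separate analyses by stratum do not contain it either, because significance in one stratum but not in the other is not evidence that the effects differ.

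At stake is whether one of the trial's two numbered aims can be answered from the stated analysis, and whether a reader can tell how much power the trial has for it.

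**Working it through.** **Inputs.** From section 7: 300 per group, two-sided alpha 0.05, overall rates 10% vs 4%, stratum rates 10% vs 1%, odds ratio (OR) 10.0, equal split. From section 8: 14.6% vs 6.7%. Assumptions: two strata, hence 150 per arm per stratum; equal control rates in both; no dropout.

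**1. The stated 85%, read as a treatment effect inside one stratum (10% vs 1%, 150 per arm).**

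- Pooled z: mean rate 0.055. Null SE = √(2 × 0.055 × 0.945 / 150) = 0.0263. Alternative SE = √((0.09 + 0.0099) / 150) = 0.0258. Power = Φ((0.09 − 1.96 × 0.0263) / 0.0258) = Φ(1.49) = 93%.
- Wald on the log OR: ln 11.0 = 2.398. SE = √(1/13.5 + 1/1.485) = 0.865. Power = Φ(2.774 − 1.96) = 79%.
- 10% vs 1% is an OR of 11.0. With the OR exactly 10.0 (10% vs 1.1%), the figures are 92% and 79%.
- A continuity correction gives 89% (88% at OR 10.0), and Fisher's exact test 94%.

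None of these gives 85%.

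**2. The stated 85%, read as a test that the ORs differ, with no effect in the other stratum.** With OR 10.0 in one stratum and 1.0 in the other, simulation gives about 85% by Breslow-Day and about 87% by likelihood ratio; the Wald formula gives 71%. So 85% is roughly reproduced. The implied overall treated rate is (1% + 10%) / 2 = 5.5%, whereas the plan assumes 4%.

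**3. Moderation power when the strata average to the planned 4%.** If one equal stratum has 1%, the other must have 2 × 4% − 1% = 7%. The ratio of ORs is 11.0 / 1.476 = 7.45, and ln 7.45 = 2.008. SE = √(1/13.5 + 1/1.485 + 1/13.5 + 1/9.765) = 0.961. Wald power = Φ(2.089 − 1.96) = 55%.

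The table sets this beside other alternatives, which are illustrative because the documents give no second-stratum effect.

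| Stratum A vs stratum B (control/treated) | Ratio of ORs | Wald | Likelihood ratio |
|---|---|---|---|
| 10/1 vs 10/10 | 11.0 | 72% | 88% |
| 10/1 vs 10/7 (averages to 4%) | 7.45 | 55% | 70% |
| 10/2 vs 10/6 (averages to 4%) | 3.13 | 31% | 35% |
| 10/1 vs 10/4 | 4.13 | 29% | 37% |
| 10/4 vs 10/10 | 2.67 | 34% | 36% |
| 14.6/6.7 vs 14.6/14.6 | 2.38 | 39% | 40% |

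Breslow-Day gives about 66% for 10/1 vs 10/7. Where a 1% cell is present, some cell is empty in 22% to 23% of trials, which is why the tests diverge. The likelihood-ratio test is slightly liberal here: its size is 0.058 with 10/4 in both strata and 0.067 with 10/1 in both.

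**4. What separate stratum tests would do when there is no moderation.** Take 10% vs 4% in both strata, 150 per arm. Pooled-z power per stratum is Φ((0.06 − 1.96 × 0.0295) / 0.0293) = 53%. The chance that exactly one stratum is significant is 2 × 0.53 × 0.47 = 50%. With section 8's rates, power per stratum is 60%, and the chance is 2 × 0.60 × 0.40 = 48%.

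**The case against.** The strongest reply is that the stratified analysis is the plan's answer to Aim 2. The term can include a homogeneity test, and the 85% may be that test's power. This has weight: the homogeneity reading comes closer to 85% than the within-stratum one. A reader might infer that the plan gives no power for moderation, or that the 85% certainly belongs to a different contrast. The documents do not support either statement. Equally, they do not establish the homogeneity reading: no such test is named, the sentence on rates describes two rates rather than two effects, and the required second stratum conflicts with the planned 4%.

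A second reply is that the moderators may be defined in the STRATEGY section or the appendix. That is possible. A reader might infer that the choice stays open until the data are seen, but this cannot be known from the supplied text. What can be said is that the supplied text cites those places for measures and data fields, not for an Aim 2 analysis.

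Third, the alternatives in the table are not the sponsor's. They show how far power depends on an unstated second-stratum effect; they do not measure an error. That stands.

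**Conclusion.** The point holds in this form. The analysis in section 7 does not, as written, compare treatment effects between strata, and the supplied text gives Aim 2 a domain but no operational variable or cut-point. If separate stratum tests were used to judge moderation, an identical 10% vs 4% effect would produce one significant and one non-significant stratum in about half of trials. The plan does not say that it would judge Aim 2 this way, but nothing in the supplied text rules it out.

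The contrast behind the 85% is ambiguous. On the reading that roughly reproduces it, the assumption is no effect in the other stratum, which does not fit the overall 10% vs 4%. With 1% and 7%, which do fit, power for moderation is about 55% (Wald), 66% (Breslow-Day) or 70% (likelihood ratio). These figures rest on two equal strata, equal control rates and no dropout; losses or an unequal split would generally lower them. The primary treatment comparison is not affected.

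**What to change.** In section 7:

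1. Name the health/SES moderator(s) with their coding or cut-points, or point to where these are defined.
2. Test Aim 2 by a prespecified treatment-by-moderator interaction in the full-sample logistic model. Name the test; a likelihood-ratio, penalised or exact test is preferable if cells are sparse.
3. Report the ratio of odds ratios with its 95% CI, and present stratum-specific odds ratios as descriptive.
4. State which contrast, and which second-stratum rate, the 85% assumes.
5. Restate the power for moderation on alternatives consistent with the overall 10% vs 4%, or label Aim 2 exploratory.

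The cost is a few lines of text and one extra term per moderator in a model already planned. No more participants are needed, and no new data if the moderators are among the fields already collected, which the unsupplied appendix would show. The downside is a less favourable stated power for Aim 2 under most alternatives. With more than one moderator, a multiplicity approach or an exploratory label is also needed.
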